3.29 Change in the Connor-Davidson Resilience Scale from baseline to 32 weeks after first group session	The participant's resilience will be measured using the Connor-Davidson Resilience Scale, which includes 10 items on a 4-point scale. The Connor-Davidson Resilience Scale assesses ability to adapt to change, achievement of goals despite obstacles, and how participants handle strong feelings. Score ranges from 0 to 40, with higher scores associated with increased resiliency.
3.30 Change in the Connor-Davidson Resilience Scale from baseline to 48 weeks after first group session	The participant's resilience will be measured using the Connor-Davidson Resilience Scale, which includes 10 items on a 4-point scale. The Connor-Davidson Resilience Scale assesses ability to adapt to change, achievement of goals despite obstacles, and how participants handle strong feelings. Score ranges from 0 to 40, with higher scores associated with increased resiliency.
3.31 Change in the Contextualized Stress Measure from baseline to 16 weeks after first group session	The participant's racial and gendered stress exposure will be measured using the Contextualized Stress Measure, which includes 69 items on a 5-point scale. The Contextualized Stress Measure is divided into six subscales, including race/racism, burden, personal history, workplace, coping and support, and stress states. Score ranges from 0 to 345, with higher scores associated with increased stress exposure.
3.32 Change in the Contextualized Stress Measure from baseline to 32 weeks after first group session	The participant's racial and gendered stress exposure will be measured using the Contextualized Stress Measure, which includes 69 items on a 5-point scale. The Contextualized Stress Measure is divided into six subscales, including race/racism, burden, personal history, workplace, coping and support, and stress states. Score ranges from 0 to 345, with higher scores associated with increased stress exposure.
3.33 Change in the Contextualized Stress Measure from baseline to 48 weeks after first group session	The participant's racial and gendered stress exposure will be measured using the Contextualized Stress Measure, which includes 69 items on a 5-point scale. The Contextualized Stress Measure is divided into six subscales, including race/racism, burden, personal history, workplace, coping and support, and stress states. Score ranges from 0 to 345, with higher scores associated with increased stress exposure.
3.34 Change in the Diet Self Efficacy Scale from baseline to 16 weeks after first group session	The participant's perceived self-efficacy for healthy eating will be measured using the Diet Self-Efficacy scale, which includes 11 items on a 5-point scale. The Diet Self Efficacy Scale assesses high caloric food temptations, social and internal factors, and negative emotional events which

OUTCOMES	ENDPOINTS
	impact eating behaviors. Scores range from 0 to 44, with higher perceived self-efficacy for healthy eating.
3.35 Change in the Diet Self Efficacy Scale from baseline to 32 weeks after first group session	The participant's perceived self-efficacy for healthy eating will be measured using the Diet Self-Efficacy scale, which includes 11 items on a 5-point scale. The Diet Self Efficacy Scale assesses high caloric food temptations, social and internal factors, and negative emotional events which impact eating behaviors. Scores range from 0 to 44, with higher perceived self-efficacy for healthy eating.
3.36 Change in the Diet Self Efficacy Scale from baseline to 48 weeks after first group session	The participant's perceived self-efficacy for healthy eating will be measured using the Diet Self-Efficacy scale, which includes 11 items on a 5-point scale. The Diet Self Efficacy Scale assesses high caloric food temptations, social and internal factors, and negative emotional events which impact eating behaviors. Scores range from 0 to 44, with higher perceived self-efficacy for healthy eating.
3.37 Change in the Self Efficacy for Exercise Scale from baseline to 16 weeks after first group session	The participant's perceived self-efficacy for healthy exercise will be measured using the Self-Efficacy for Exercise Scale, which includes 9 items on a 11-point scale. Scores range from 0 to 90, with higher scores associated with higher self-efficacy for exercise.
3.38 Change in the Self Efficacy for Exercise Scale from baseline to 32 weeks after first group session	The participant's perceived self-efficacy for healthy exercise will be measured using the Self-Efficacy for Exercise Scale, which includes 9 items on a 11-point scale. Scores range from 0 to 90, with higher scores associated with higher self-efficacy for exercise.
3.39 Change in the Self Efficacy for Exercise Scale from baseline to 48 weeks after first group session	The participant's perceived self-efficacy for healthy exercise will be measured using the Self-Efficacy for Exercise Scale, which includes 9 items on a 11-point scale. Scores range from 0 to 90, with higher scores associated with higher self-efficacy for exercise.
3.40 Change in amount of moderate to vigorous physical activity from baseline to 16 weeks after first group session	The participant's moderate to vigorous physical activity will be measured by triaxial accelerometry. Results will be reported in minutes, with higher numbers indicating a higher amount of moderate to vigorous physical activity.
3.41 Change in amount of moderate to vigorous physical activity from baseline to 32 weeks after first group session	The participant's moderate to vigorous physical activity will be measured by triaxial accelerometry. Results will be reported in minutes, with higher numbers indicating a higher amount of moderate to vigorous physical activity.
3.42 Change in the dietary risk assessment score from baseline to 16 weeks after first group session	The participant's dietary intake will be assessed using the dietary risk assessment, which includes 54 items. The dietary risk assessment measures the healthiness of a participant's eating habits. Score ranges from 0 to 108, with higher scores associated with less healthy dietary intake.

OUTCOMES	ENDPOINTS
3.43 Change in the dietary risk assessment score from baseline to 32 weeks after first group session	The participant's dietary intake will be assessed using the dietary risk assessment, which includes 54 items. The dietary risk assessment measures the healthiness of a participant's eating habits. Score ranges from 0 to 108, with higher scores associated with less healthy dietary intake.
3.44 Change in veggie meter score from baseline to 16 weeks after first group session	The participant's nutrition will be assessed using the veggie meter, which uses light reflectance spectroscopy to provide an estimate skin carotenoid composite score. Score ranges from 0 to 800, with higher scores associated with greater fruit and vegetable intake.
3.45 Change in veggie meter score from baseline to 32 weeks after first group session	The participant's nutrition will be assessed using the veggie meter, which uses light reflectance spectroscopy to provide an estimate skin carotenoid composite score. Score ranges from 0 to 800 with higher scores associated with greater fruit and vegetable intake.
3.46 Change in BMI from baseline to 16 weeks after first group session	The participant's BMI is calculated as weight (kg) divided by height (cm).
3.47 Change in BMI from baseline to 32 weeks after first group session	The participant's BMI is calculated as weight (kg) divided by height (cm).
3.48 Change in weight from baseline to 16 weeks after first group session	The participant's weight will be measured using a digital scale.
3.49 Change in weight from baseline to 32 weeks after first group session	The participant's weight will be measured using a digital scale.
3.50 Change in waist-to-hip ratio from baseline to 16 weeks after first group session	The participant's waist to hip ratio is calculated by using the mean of two waist circumference measurements divided by mean of two hip circumference measurements. Waist circumference will be measured at the midpoint between the upper iliac crest and lower costal margin in the midaxillary line. Hip circumference will be measured at the maximum width of the buttocks or gluteo-femoral fold.
3.51 Change in waist-to-hip ratio from baseline to 32 weeks after first group session	The participant's waist to hip ratio is calculated by using the mean of two waist circumference measurements divided by mean of two hip circumference measurements. Waist circumference will be measured at the midpoint between the upper iliac crest and lower costal margin in the midaxillary line. Hip circumference will be measured at the maximum width of the buttocks or gluteo-femoral fold.
3.52 Change in blood pressure (systolic blood pressure/diastolic blood pressure) from baseline to 16 weeks after first group session	The participant's blood pressure is measured using an electronic sphygmomanometer. The final measurement will be the mean of three measurements.
3.53 Change in blood pressure (systolic blood pressure/diastolic blood pressure) from baseline to 32 weeks after first group session	The participant's blood pressure is measured using an electronic sphygmomanometer. The final measurement will be the mean of three measurements.
3.54 Change in high sensitivity C-reactive protein amount from baseline to 16 weeks after first group session	The participant's high sensitivity C-reactive protein levels will be obtained via phlebotomy.

OUTCOMES	ENDPOINTS
3.55 Change in high sensitivity C-reactive protein amount from baseline to 32 weeks after first group session	The participant's high sensitivity C-reactive protein levels will be obtained via phlebotomy.
3.56 Change in IL-6 amount from baseline to 16 weeks after first group session	The participant's IL-6 levels will be obtained via phlebotomy.
3.57 Change in IL-6 amount from baseline to 32 weeks after first group session	The participant's IL-6 levels will be obtained via phlebotomy.
3.58 Change in glycosylated hemoglobin amount from baseline to 16 weeks after first group session	The participant's glycosylated hemoglobin levels will be obtained via phlebotomy.
3.59 Change in glycosylated hemoglobin amount from baseline to 32 weeks after first group session	The participant's glycosylated hemoglobin levels will be obtained via phlebotomy.

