3 OUTCOMES AND ENDPOINTS

OUTCOMES	ENDPOINTS
Primary	
1.1 Change in amount of moderate to vigorous physical activity from baseline to 48 weeks after first group session	The participant's moderate to vigorous physical activity will be measured by triaxial accelerometry. Results will be reported in minutes, with higher numbers indicating a higher amount of moderate to vigorous physical activity.
1.2 Change in the dietary risk assessment score from baseline to 48 weeks after first group session	The participant's dietary intake will be assessed using the dietary risk assessment, which includes 54 items. The dietary risk assessment measures the healthiness of a participant's eating habits. Score ranges from 0 to 108, with higher scores associated with less healthy dietary intake.
1.3 Change in veggie meter score from baseline to 48 weeks after first group session	The participant's nutrition will be assessed using the veggie meter, which uses light reflectance spectroscopy to provide an estimate skin carotenoid composite score. Score ranges from 0 to 800, with higher scores associated with greater fruit and vegetable intake.
Secondary	
2.1 Change in BMI from baseline to 48 weeks after first group session	The participant's BMI is calculated as weight (kg) divided by height (cm).
2.2 Change in weight from baseline to 48 weeks after first group session	The participant's weight will be measured using a digital scale.
2.3 Change in waist-to-hip ratio from baseline to 48 weeks after first group session	The participant's waist to hip ratio is calculated by using the mean of two waist circumference measurements divided by mean of two hip circumference measurements. Waist circumference will be measured at the midpoint between the upper iliac crest and lower costal margin in the midaxillary line. Hip circumference will be measured at the maximum width of the buttocks or gluteo-femoral fold.
2.4 Change in percent body fat from baseline to 48 weeks after first group session	The participant's percent body fat is measured using lange skinfold calipers. The final measurement will be the mean of three measurements on the right side of the body.
2.5 Change in in blood pressure (systolic blood pressure/diastolic blood pressure) from baseline to 48 weeks after first group session	The participant's blood pressure is measured using an electronic sphygmomanometer. The final measurement will be the mean of three measurements.

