5 STUDY POPULATION

5.1 INCLUSION CRITERIA

To be eligible to participate in this study, an individual must meet all the following criteria:

1. Self-reported African American or Black woman
2. BMI= 25-39 kg/m² (confirmed at baseline assessment)
3. At least one cardiometabolic risk factor:
 - a. < 150 minutes of self-reported moderate to vigorous exercise per week
 - b. History of gestational diabetes
 - c. Parent or sibling with prediabetes or diabetes
 - d. Personal or family history of hypertension ($\geq 130/80$)
 - e. Prediabetes or impaired glucose metabolism ($\text{HgbA1c}=5.7\text{-}\leq 6.5$)
 - f. Personal or family history of abnormal cholesterol levels
4. At least 18 years of age
5. Able to read/speak English

6. Willing to attend scheduled classes, complete internet surveys and biomarker assessments
7. Able/willing to engage in moderate to vigorous exercise
8. Ambulatory
9. Superwoman Schema Questionnaire score indicating at least moderate endorsement of one or more subscales (strength: 7; emotional suppression: 7; resistance of vulnerability: 8; motivation to succeed: 7; or helping others: 10) or a total score of 20 or greater.
10. A Perceived Stress Scale-14 score of >5 or self-report at least “some” general stress.
11. Willing to agree to be randomized between the two culturally-tailor programs.
12. Willing to not share group assignment for the study.

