For the purposes of this study, the participant's moderate to vigorous physical activity will be measured. Moderate to vigorous physical activity is defined as activities that are strenuous enough to burn off three to six times as much energy per minutes as one does when sitting quietly, or exercises that clock in at 3 to 6 METs.

Dietary Risk Assessment

The participant's dietary intake will be assessed using the dietary risk assessment, which includes 54 items. The dietary risk assessment measures the healthiness of a participant's eating habits. Score ranges from 0 to 108, with higher scores associated with less healthy dietary intake.

This questionnaire will be performed at baseline and 16, 32, and 48 weeks post first group session. The data will be entered electronically by the patient through REDCap survey; however, paper copies of the questionnaire may be used if necessary.

Veggie Meter

The participant's fruit and vegetable intake will be measured by the participant's skin carotenoids. The Veggie Meter uses a pressure-mediated reflection spectroscopy device to measure these carotenoids. Study personnel will calibrate the Veggie Meter as needed, and then ask the participant to wash their hands with soap and water. The participant will then place their finger in the cradle of the meter, and will hold it there until the scan is complete.

The Veggie Meter procedure will be performed at baseline and 16, 32, and 48 weeks post first group session.

Weight and Height

The participant's weight will be measured using an electronic scale. Weight will be converted to kilograms to calculate participant BMI. The participant's height will be measured to the nearest centimeter to calculate participant BMI.

Weight will be performed at baseline and 16, 32, and 48 weeks post first group session. Height will be performed at baseline, and is optional to perform at 16, 32, and 48 weeks post first group session.

Hip Circumference

Hip circumference will be measured at the maximum width of the buttocks or gluteo-femoral fold. Two measurements will be recorded by study personnel. The mean of these measurements will be used for the waist-to-hip ratio.

Hip circumference will be measured at baseline and 16, 32, and 48 weeks post first group session.

Waist Circumference

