The primary endpoint at 48 weeks post first group session is tested at a significance level of 0.05; the other two timepoints will be tested using a Bonferroni correction of a two-sided 0.025 ($=0.05/2$) significance level. A compound symmetry correlation structure is assumed across all timepoints in our calculations. Based on pilot data, correlation parameters are 0.35 for BMI, 0.11 for WHR and -0.45 for A1C. With 80 participants per group (total of 160), statistical power is 85% to detect an effect size of 0.56 for BMI and exceeds 95% to detect an effect size of 0.45 for A1C and 0.59 for waist-hip ratio at each post-baseline time point.^{76,94} In tertiary endpoints, it is hypothesized that mediation of the intervention effect on the primary outcomes (exercise and healthy eating) by the tertiary outcomes (improvements in self-reported mindfulness, stress management, positive reappraisal, self-regulation, and self-efficacy). [In simulations of power for mediation tests, Fritz and Mackinnon⁹⁵ found that when effect sizes (standardized regression coefficients) relating the intervention to the mediator and the mediator to the outcome are all ≥ 0.26 (small- medium, according to Cohen's [1988] definition)⁹⁶, the sample size ($n=160$)

is adequate for at least 80% power. If either effect size is much smaller (simulations used 0.14), the study will be underpowered.

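### Outcomes 2.1, 3.46 and 3.47 define BMI as weight (kg) over unsquared height (cm), which is not BMI and conflicts with the kg/m² inclusion criterion

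*Combined protocol and SAP*

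**What the plan says.** The outcomes table in section 3 of the protocol carries the definition three times, in the same words: secondary outcome 2.1, and exploratory outcomes 3.46 and 3.47. Each says that "BMI is calculated as weight (kg) divided by height (cm"). Together they cover all three follow-up visits.

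Three other places bear on the definition:

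- Section 5.1, inclusion criterion 2, sets the eligible range as "BMI= 25-39 kg/m² (confirmed at baseline assessment").
- Section 8.1, under Weight and Height, fixes the inputs: "Weight will be converted to kilograms to calculate participant BMI", and "height will be measured to the nearest centimeter to calculate participant BMI". It gives recording units but no formula.
- The same part of section 8.1 says "Height will be performed at baseline, and is optional to perform at 16, 32, and 48 weeks post first group session". The schedule of activities in section 1.2 likewise requires height at baseline only. Neither says which height enters BMI at a follow-up visit where height was measured again.

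BMI is named among the secondary endpoints in section 9.4.3. It also appears in section 9.2, where "statistical power is 85% to detect an effect size of 0.56 for BMI".

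**The concern.** An endpoint definition is what a programmer implements and what a results table cites. This one departs from BMI in two ways: the height is in centimetres rather than metres, and it is not squared. The protocol therefore uses one name for two quantities, one to decide who enters the trial and another to measure change in those who entered.

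Reported results are what is at stake. If the formula were followed, the baseline and follow-up values, the change scores and the unit label would all be wrong. They would not be comparable with the eligibility range or with BMI reported elsewhere. Section 10.1.9 commits the trial to submitting results to a public registry, and section 9.4.7 plans listings of individual data by measure for sharing, so the error would carry into both. Section 8.1 has the raw inputs in exactly the units of the faulty formula (kg and cm), which makes it easier for the formula to be copied into code unchallenged.

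**Working it through.** **Inputs.** The stated formula is from section 3. The eligible range, 25 to 39 kg/m², is from section 5.1. The documents give no participant heights or weights, so those used below are assumptions: heights from 150 to 180 cm, and weights chosen to illustrate.

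**1. One woman, both formulas (assumed 80 kg, 165 cm).**
- As stated: 80 / 165 = 0.485.
- BMI: 80 / 1.65² = 80 / 2.7225 = 29.4 kg/m².

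**2. The eligible range under the stated formula.** For BMI *B* and height *h* in cm, weight is *B* × (*h*/100)². Dividing by *h* gives the stated quantity, *B* × *h* / 10,000.

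| Height | BMI 25 becomes | BMI 39 becomes |
|---|---|---|
| 150 cm | 0.375 | 0.585 |
| 165 cm | 0.413 | 0.644 |
| 180 cm | 0.450 | 0.702 |

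No value is near 25 to 39. To score 25 to 39 by the stated formula, a woman of 165 cm would have to weigh 25 × 165 = 4,125 kg to 39 × 165 = 6,435 kg.

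**3. Could a single slip explain it?** Correcting only one of the two faults does not recover the range:
- Metres without squaring (kg/m) gives 37.5 (BMI 25 at 150 cm) to 70.2 (BMI 39 at 180 cm).
- Squaring without metres (kg/cm²) gives 0.0025 to 0.0039.

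A superscript lost when the PDF was read would therefore not account for it. The superscript in section 5.1 did survive.

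**4. Is it a constant rescaling?** BMI divided by the stated quantity is 10,000 / *h*: 66.7 at 150 cm, 60.6 at 165 cm and 55.6 at 180 cm. It is not one constant. For example, 75 kg at 150 cm and 90 kg at 180 cm both score 0.500 as stated, but their BMIs are 75 / 2.25 = 33.3 and 90 / 3.24 = 27.8. Correct results cannot be recovered from summary tables by one multiplier. They can be recovered from individual weight and height.

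**5. Does the between-arm test move?** If baseline height is used throughout, each formula divides a woman's weight by a number fixed for her, and randomization balances height between arms in expectation. A simulation used 80 women per arm, a baseline-adjusted comparison, BMI 25 to 39, mean height 163 cm with SD 5, 6.5 or 8 cm, a percentage weight change with SD 5%, and a treatment effect giving about 83% power. Apart from the 80 per arm and the BMI range, these are assumptions. In 2,000 trials per scenario the two change scores correlated at about 0.999, the powers agreed within 0.3 percentage points, and the decision at p < 0.05 differed in about 1% of trials.

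**6. The optional follow-up height.** At an assumed 80 kg, a recorded height of 164 rather than 165 cm gives 80 / 1.64² = 29.74 instead of 29.38. BMI moves by about 0.36 kg/m² with no change in weight.

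**The case against.** The best defence is that nobody would program this literally. The endpoint is called BMI, which is a standard quantity. Section 5.1 gives its unit and has it confirmed at baseline, so staff must calculate true BMI for every woman before randomization. Values of about 0.4 to 0.7 would be recognised at once as wrong. Section 8.1 suggests how the slip arose: the recording unit for height was carried into a shortened definition. Weight is also analysed on its own as outcome 2.2. All of this is fair, and a drafting error is much the likeliest explanation. It limits the practical risk, but the only formula in the plan is still wrong.

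A reader might infer two stronger conclusions that the documents do not support:

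- **That the BMI power statement in section 9.2 is undermined.** The 0.56 for BMI is listed beside 0.45 for A1C and 0.59 for waist-hip ratio. Across three variables on such different scales, these read as standardized, unit-free effects. The correlation of 0.35 is attributed to pilot data. Neither figure depends on the formula in section 3.
- **That the treatment comparison would be materially distorted.** Two individuals of very different height can diverge noticeably: an assumed 5 kg loss at 150 versus 175 cm is 2.22 versus 1.63 kg/m² (ratio 1.36), but 0.0333 versus 0.0286 kg/cm (ratio 1.17). That comparison concerns two people, not two randomized arms. Step 5 of the check shows that the arm-level test hardly changes under reasonable assumptions.

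**Conclusion.** The definition is wrong as written. Outcomes 2.1, 3.46 and 3.47 do not define BMI, they contradict the kg/m² criterion in section 5.1, and nothing elsewhere in the plan corrects them. If followed, reported values would be too small by a factor of roughly 56 to 67 over heights of 180 down to 150 cm, with the wrong unit and no single conversion factor.

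The reach is limited. One secondary outcome and two exploratory outcomes are affected. The primary endpoints and the section 9.2 power statement are not, and the effect on the between-arm BMI test is probably negligible. That last judgement rests on baseline height being used throughout and on the assumed height and weight-change distributions in the simulation. The factor range rests only on the assumed span of heights. The contradiction between sections 3 and 5.1 needs no assumption.

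**What to change.** In outcomes 2.1, 3.46 and 3.47 of section 3, replace the formula with weight (kg) divided by [height (m)] squared, reported in kg/m². For programming from the recorded units this is weight (kg) / [height (cm) / 100]². At 165 cm, weights of 68.1 and 106.2 kg then return 25.0 and 39.0, matching section 5.1.

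As a secondary clarification, add one sentence to the Weight and Height part of section 8.1 saying that the baseline height is used to calculate BMI at every visit, because later height is optional.

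The cost is three identical wording corrections and one added sentence. The design, sample size, visit procedures and data to be collected stay as they are.
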